
	
count of COPD exacerbations combined with CAT total score and mMRC score. GOLD categories are mutually exclusive. Results will be presented overall and by treatment cohort (FLUT/SAL or UMEC/VI).
 
Multivariable modeling of the primary objective will be conducted following review of descriptive and IPTW results. Each model will examine the relationship between symptom burden and treatment with FLUT/SAL or UMEC/VI. The dependent variable for the models will be CAT total score and mMRC score, respectively; covariates for the models will be based on clinical and analytic significance.

Sample Size and Power
	
The study sample is estimated to include 385 patients per cohort with evidence of COPD diagnosis and single-inhaler dual therapy treatment with FLUT/SAL or UMEC/VI. A sample size of n=385 per cohort is required to assess statistical significance with a 95% confidence interval at ± 0.05 with 80% power. A sampling frame of 2,700 patients is estimated to be used to reach the target evaluable sample size, n=770 patients (385/cohort). Based on patient counts and response rate estimates, it is anticipated that two waves of data collection will be needed to meet the target sample size.
 
This estimated study sample size is sufficient to detect proportional differences in PRO outcomes between two cohorts of patients (i.e., patients treated with FLUT/SAL or UMEC/VI who have severe symptoms as measured by a CAT total score ≥ 10 or an mMRC score ≥ 2); other stratifications tied to primary and secondary endpoints may be considered for statistically powered analyses as sample size allows.

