4.4 Inverse Probability of Treatment Weighting

To address the objective of comparing symptom burden of patients by treatment cohort (FLUT/SAL as compared to UMEC/VI), inverse probability of treatment weighting will be applied to reduce confounding on observed clinical, demographic, and sociodemographic characteristics shown in Appendix 4 (Section 11). The goal of adjusting for differences in non-treatment characteristics between treatment cohorts is to balance the distribution of covariates that would occur if participants were randomly assigned to treatment cohorts *a priori*.^{xiv} The weights in IPTW are based on each individual's probability of receiving a specific treatment given the confounders, which is known as the propensity score (PS). Use of methods that make adjustments via propensity scores is an appropriate way to create balance in the covariate distribution among cohorts.^{xv,xvi, xvii}

A logistic regression will be employed with a dependent or response that is conditioned on a set of predetermined covariates. Each subject will be assigned a propensity score weight and the adjustment for potential treatment selection bias will be made by weighting the expected value of an outcome or outcomes of interest in the corresponding multivariable model by a function of the inverse propensity score and sample size of the cohort.^{xviii}

The study team will examine the quality of the propensity score determination via descriptive techniques (e.g., examination of the overlap in histograms of the respective cohort propensity score distributions, and assessment of goodness of fit of the logistic regression) to ensure the weighting approach is sound. Following review of these diagnostics, the study team will identify the characteristics of any outliers and will determine whether those subjects should remain in the model based on their clinical and analytic characteristics and whether these characteristics would unduly impact subsequent multivariable analysis. The p values determined from the weighted and unweighted descriptive analysis of covariates included in the IPTW analysis will be compared.

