4.5 Multivariable Analysis

Multivariable analysis of the primary objective will be conducted using appropriate regression models (e.g., ordinary least squares [OLS], logistic regression, generalized linear models [GLM], negative binomial regression, Poisson [log-linear] regression) based on the distribution of the measure.

Two multivariable models are planned for the study. Final outcomes for the multivariable analysis will be selected jointly by Optum and GSK after review of descriptive results, including PRO scores, IPTW results, utilization, and costs. Specific predictors to be included in the models will be determined based upon clinical rationale and statistical significance. In general, the statistical significance of each predictor variable will be examined in the univariate regression analysis. Variables that demonstrate at least marginal statistical significance ($p < 0.1$) in univariate analysis will be included in the multivariate models, along with relevant clinical variables regardless of their statistical significance.

Multivariable analyses to assess the primary objective are outlined here. The dependent variable of the first model will be the CAT total score, and the dependent variable of the second model will be the mMRC score. Each model will examine the relationship between symptom burden and treatment (FLUT/SAL or UMEC/VI). Each model will include clinically and analytically meaningful covariates based on the IPTW analysis; it is assumed that the covariates will be the same for each model.

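### Section 4.4 lets the study team drop undefined propensity-score outliers case by case from the primary comparison, with no fixed rule and no analysis that keeps all subjects

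*Combined protocol and SAP*

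**What the plan says.** Section 3.2.2 explains that the cohorts cannot be matched when the sample is identified, and relies on inverse probability of treatment weighting (IPTW) to handle confounding. Section 4.4 specifies the weighting.

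- **Score model.** "A logistic regression will be employed with a dependent or response that is conditioned on a set of predetermined covariates". The covariates are listed in Appendix 4.
- **Diagnostics.** The team inspects the overlap of the propensity histograms and the fit of the logistic model.
- **Removal.** The removal step is tied to these checks, and the decision is left to judgement: the team "will determine whether those subjects should remain in the model based on their clinical and analytic characteristics". A second criterion is "whether these characteristics would unduly impact subsequent multivariable analysis".
- **Balance.** "The p values determined from the weighted and unweighted descriptive analysis of covariates included in the IPTW analysis will be compared". No other balance measure is named.

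On timing, the Protocol Synopsis says: "Multivariable modeling of the primary objective will be conducted following review of descriptive and IPTW results". Section 4.5 has the final outcomes for the multivariable analysis chosen "after review of descriptive results, including PRO scores, IPTW results, utilization, and costs". Section 4.5 also provides for a further look at outliers in the fitted outcome models, with no rule for handling them.

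Several other sections leave definitions to a later SAP (for example 3.3.2 and 4.2). Section 4.4 does not do so for this step.

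**The concern.** IPTW removes confounding by giving large weights to patients whose treatment is unlike what their covariates predict. These patients restore the balance. If they are the ones classed as outliers and removed, and the score is left as it was, the weighted cohorts drift back toward the unweighted ones and the estimate drifts toward the crude difference.

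The second problem is freedom of choice. The plan does not say how many subjects may go, on what cut-off, or who must be blind to what. One removal criterion looks ahead to the effect on the outcome model. Several candidate analysis sets are therefore possible, and a choice among them can inflate the type I error even when each one is unbiased.

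At stake is the primary objective, the comparison of CAT and mMRC between UMEC/VI and FLUT/SAL.

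**Working it through.** **1. The plan's own figure.** Section 3.5 sets 385 surveys per cohort from a 95% interval of ±0.05 at a proportion of 0.5: n = 1.96² × 0.5 × 0.5 / 0.05² = 384.15, rounded up to 385. This reproduces. It does not depend on the present point, but it gives the simulation size, 2 × 385 = 770.

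**2. What the team can see.** Section 3.1.6 merges survey and claims data into one analytic file. Appendix 4 puts survey items (general health, BMI, smoking, income, education) into the score model, so the score cannot be fitted before the survey data are in hand. No blinding to CAT or mMRC is stated. Outcomes can therefore be visible when removal is decided. Nothing says that they have been reviewed.

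**3. Main simulation.** All inputs below except n are assumptions; the documents give no figure for confounding or CAT variability.

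- 770 subjects, 1,500 data sets, true effect 0.
- Four standard-normal covariates. Propensity coefficients 0.4, 0.3, -0.3 and 0. Effects on CAT of 2, 1.5, 0 and 1. Residual SD 7.
- The first two covariates are the confounders. Their contributions to the crude difference are roughly in the ratio 0.4 × 2 = 0.80 to 0.3 × 1.5 = 0.45, that is 64% to 36%. The simulated crude difference is 1.16 CAT points.
- Weighted linear model with robust (HC1) standard errors; score not refitted unless stated.

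Bias in CAT points after removing the largest 1%, 2% or 5% of weights (about 8, 15 or 38 subjects):

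| Outcome model | 1% | 2% | 5% | Type I error, smallest p over the options |
|---|---|---|---|---|
| Treatment only | 0.25 | 0.42 | 0.80 | 29% |
| One confounder (the stronger) adjusted | 0.10 | 0.17 | 0.33 | 13% |
| All confounders adjusted | 0.00 | 0.00 | 0.00 | 9% |

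- Treatment-only type I error for the three single deletions: 8%, 13% and 27%. With all subjects kept it is 3%, with bias 0.00.
- As a share of the crude difference: 0.25/1.16 = 22%, 0.42/1.16 = 36%, 0.80/1.16 = 69%.
- The middle row agrees with the 36% of confounding left unadjusted: 0.36 × 0.80 = 0.29, against 0.33 simulated. If only the weaker confounder were adjusted, about 0.64 × 0.80 = 0.51 would remain at 5%.
- Treatment only with the score refitted after removal: 0.08, 0.14, 0.28.
- Treatment only, subjects outside common support removed (about 10 of 770), no refit: -0.06, type I error 3%.
- Treatment only, weights capped at the 1st and 99th percentiles, nobody removed: 0.05, type I error 3 to 4%.
- Monte Carlo standard error at 29%: √(0.29 × 0.71 / 1,500) = 1.2 percentage points.

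**4. Second set-up.** 770 subjects, 1,000 runs, three confounders worth 2 CAT points per SD each, residual SD 7, treatment-only comparison. Bias for moderate / strong treatment selection:

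| Handling | Moderate | Strong |
|---|---|---|
| Unweighted | 1.94 | 3.29 |
| IPTW, all kept | -0.01 | 0.04 |
| 8 largest weights removed, no refit | 0.44 | 0.89 |
| Same, refitted | 0.15 | 0.54 |
| 20 largest removed, no refit | 0.84 | 1.49 |
| Propensity limited to 0.1-0.9, refitted | -0.01 | 0.02 |
| Capped at 99th percentile | 0.07 | 0.33 |

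After the 8 largest weights are removed without refit, the standardized difference on a confounder rises from 0.00 to 0.07 (moderate) or 0.155 (strong). A balance re-check on that scale would show the loss.

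**The case against.** A reader might infer that subjects will be deleted after the results have been seen, and that this undoes the IPTW adjustment. The documents do not support either statement in that form.

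- **Timing.** The trigger in Section 4.4 is the propensity diagnostics. The passage in Section 4.5 about a review of PRO scores concerns the choice of outcomes for the models, not the removal of subjects. This stands: visibility of outcomes is a possibility left open, not a stated step.
- **Who is removed.** The text speaks of outliers and does not name weights. Histogram overlap points at least as naturally to trimming outside common support, which gave almost no bias above. This stands. Large weights are a reasonable reading, but not the only one.
- **Refitting.** The plan does not say the score would be left unrefitted. With refit the treatment-only bias falls to 0.08 to 0.28.
- **The planned model.** Section 4.4 applies the weights within a multivariable model and Section 4.5 adds covariates to it. With every confounder included, deletion bias vanishes. This is the strongest objection and it stands for a fully adjusted model. It is not secured by the plan: covariates enter by univariate p < 0.1, clinical relevance and review of the IPTW results, and a weighted comparison without covariates would stay exposed.
- **Deletion fractions.** The 1%, 2% and 5% are illustrative. The largest stabilised weight in the main set-up averages about 3.3, so calling 38 subjects outliers there would be hard to defend. The upper figures are a bound, not a forecast.
- **A rule may sit elsewhere.** A later SAP could contain one, but Section 4.4 does not send the reader there for it.

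None of these supplies the missing rule. Even with full adjustment, choosing among the deletion options gave about 9% type I error against about 5%.

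**Conclusion.** The point holds as a defect in a stated rule. Subjects can leave the primary comparison by judgement, on an undefined criterion that includes their expected effect on the outcome model, without a refit, a balance re-check, blinding or an all-subjects result.

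The size depends on choices the plan leaves open. If the largest weights are removed and the score is not refitted, the bias is about 0.25 to 0.80 CAT points with treatment alone in the model, about 0.1 to 0.3 with the stronger of two confounders adjusted, and about 0 with all adjusted. Type I error from choosing among options runs from about 9% to about 29%. These figures rest on assumed confounding and an assumed residual SD of 7; stronger selection gives larger bias, and symmetric propensity trimming gives essentially none. The documents do not establish that bias will occur or that outcomes will guide the removals. They do leave both possible, and this is cheap to close before the analysis.

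**What to change.** Replace the judgement step in Section 4.4, or state the following in the SAP, before CAT and mMRC results by cohort are reviewed.

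1. A numeric rule for extreme weights, for example stabilised weights capped at the 1st and 99th percentiles, with no subject removed by judgement.
2. If trimming on a propensity range is preferred, its limits in advance and a refit of the score in the trimmed sample. Capping and trimming are both defensible; what matters is that one is fixed.
3. Standardized differences for the Appendix 4 covariates after weighting, and again after any capping or trimming, in place of relying on p values.
4. The uncapped estimate in all subjects with robust standard errors, always reported as a sensitivity analysis.

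The cost is wording and one extra analysis; no new data are needed. Capping leaves a small residual bias, about 0.05 CAT points in the main simulation (0.07 and 0.33 under moderate and strong selection in the second set-up). Trimming slightly changes the population to which the estimate applies. The standardized differences and the all-subjects result let a reader see whether either matters.

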4 DATA ANALYSIS CONSIDERATIONS

4.1 Statistical Methods

The final analysis for the study will comprise descriptive analyses of cross-sectional survey data linked to baseline claims data and multivariable modeling of the primary study outcome. Analyses will be conducted using the SAS statistical software package. Illustrative table shells and figures showing the format for the analysis results will be provided separately and will include specific statistical tests that will be undertaken in support of each study objective.

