4.3 Descriptive Analyses of Survey and Claims Data

Administrative Claims Data

Health service utilization and costs for the baseline period will be identified and presented descriptively for all-cause and COPD-related total HCRU and costs. For dichotomous variables, N (%) will be presented. For continuous variables, means, standard deviations, medians, ranges, and percentiles will be presented as appropriate. Costs will be defined as costs to the health plan and estimated costs paid by Medicare; costs will not include costs to the patient (copays, deductibles). Detailed descriptions of cost and utilization measures are provided in 3.3.2.2.

Survey Data

All study variables will be analyzed descriptively. Numbers and percents will be provided for dichotomous and polychotomous variables. Relevant measures of centrality such as means and medians will be presented for continuous measures, as well as variance measures such as standard deviations and percentiles (e.g., p25, p75). Comparisons of demographic characteristics and outcome measures will be provided. Appropriate tests (e.g., t-test, Mann Whitney-U test, chi-square test) will be used based on the distribution of the measure. For example, a one sample t-test could be used to show difference from the sample mean on a given PRO (such as CAT score) as compared to an expected value (such as CAT scores among older adults from the published literature). Pearson correlation coefficients are utilized for bivariate comparisons of CAT total score and mMRC score with selected clinical and sociodemographic characteristics.

In addition to descriptive analyses of all survey variables, survey responders and non-responders will be compared on select demographic characteristics in order to assess the generalizability of the evaluable survey sample.

Primary Objective

In order to fulfill the primary objective, the proportion of patients with low and high symptom severity will be identified based on responses to the mMRC and CAT measures. Patients may be categorized into multiple levels of severity based on the distribution of responses to one or both measures (e.g., patients with a high degree of dyspnea per the mMRC score and severe symptom burden per the CAT score may be categorized as most severe for relevant analyses).

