11 APPENDIX 4. COVARIATES OF INTEREST FOR IPTW

The following is a list of covariates planned for inclusion in the IPTW analysis. Final covariates included in the multivariable models will be determined following review of the comparison of weighted and non-weighted descriptive results as described in Sections 4.3 - 4.4.

Clinical characteristics

- General health
- BMI
- Current smoking status
- Pack years
- Years since COPD diagnosis
- Baseline Quan-Charlson comorbidity score
- Count of COPD-related comorbid conditions
- Count of all-cause baseline medication fills
- Count of COPD-related baseline medication fills
- Count of all-cause baseline ambulatory visits (office and/or outpatient)
- Count of COPD-related baseline ambulatory visits (office and/or outpatient)
- Count of baseline COPD exacerbations

Demographic and sociodemographic characteristics

- Age
- Sex
- Race
- Ethnicity
- Geographic region
- Population density
- Marital status
- Household income
- Education

ⁱ Dillman DA. Mail and Internet surveys: the tailored design method, second edition. New York: John Wiley & Sons, Inc.

ⁱⁱ Edwards P, Roberts I, Clarke M, et al. Increasing response rates to postal questionnaires: systematic review. *BMJ*. 2002;324:1183.

ⁱⁱⁱ Following the Dillman tailored design method, Optum's standard data collection time period is 8 weeks.

^{iv} Doherty, DE, Belfer, MH, Brunton, SA, Fromer, L, Morris, CM, Snader, TC. Chronic Obstructive Pulmonary Disease: Consensus Recommendations for Early Diagnosis and Treatment. *J Fam Prac*, 2006.

^v Bestall C, Paul EA, Garrod R, et al. Usefulness of the Medical Research Council (MRC) dyspnea scale as a measure of disability in patients with COPD disease. *Thorax* 1999;54:581-586.

^{vi} Jones PW, et al. Development and first validation of the COPD Assessment Test (CAT). *Eur Respir J* 2009;34(3):648-654.

^{vii} Jones PE, et al. Properties of the COPD Assessment Test (CAT) in a cross-sectional European study. *Eur Respir J* 2012; doi: 10.1183/09021936.00177210.

^{viii} Quan H, Li B, Couris CM, Fushimi K, Graham P, Hider P, Januel JM, Sundararajan V. Updating and validating the Charlson comorbidity index and score for risk adjustment in hospital discharge abstracts using data from 6 countries. *Am J Epidemiol*. 2011;173(6):676-82.

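### The only before/after check on individual covariates named in section 4.4 compares p-values, which mix imbalance with sample size and so do not measure the balance that IPTW aims for

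*Combined protocol and SAP*

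**What the plan says.** Section 4.4 says that the goal of the adjustment "is to balance the distribution of covariates that would occur if participants were randomly assigned to treatment cohorts". It then names three kinds of check:

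- overlap of the two cohorts' propensity-score histograms, which works at the level of the score;
- goodness of fit of the logistic propensity model, which works at the level of the model;
- for the covariates themselves: "The p values determined from the weighted and unweighted descriptive analysis of covariates included in the IPTW analysis will be compared".

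The first two are given as examples, and a review of outlying subjects follows them. Outcomes are to be weighted "by a function of the inverse propensity score and sample size of the cohort". Section 4.4 does not say how variances will be computed after weighting.

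The check has a later use. Appendix 4 states: "Final covariates included in the multivariable models will be determined following review of the comparison of weighted and non-weighted descriptive results", and refers back to sections 4.3 and 4.4. Section 4.5 adds a univariate screen: "Variables that demonstrate at least marginal statistical significance" (p<0.1) enter the models, together with clinically relevant variables whatever their significance.

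Section 4.3 lists means, standard deviations, percentiles and percents for the descriptive tables and says of the tests: "Appropriate tests (e.g., t-test, Mann Whitney-U test, chi-square test) will be used based on the distribution of the measure". It does not mention weighting. Section 4.1 leaves further detail to separate table shells, which "will include specific statistical tests that will be undertaken in support of each study objective". The supplied text contains no standardised difference, variance ratio or balance limit.

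**The concern.** The CAT and mMRC comparison is not randomised, the sample is a convenience sample (section 3.2.2), and IPTW is the plan's stated answer to confounding. Readers will want to know whether weighting made the cohorts alike on each of the 21 covariates in Appendix 4. A p-value answers another question: whether a difference of that size would be surprising under chance allocation at that sample size. It can be large because the difference is small or because the information is limited.

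Comparing p before and after weighting adds a second problem, because weighting can change the effective sample size as well as the imbalance. If the variance reflects the weights, p can rise with no gain in balance. If the weights are scaled to cohort size and no variance correction is made, p need not rise at all. The weighting could therefore be reported as adequate or inadequate on a measure that shows neither, and the review that sets the outcome-model covariates would rest partly on that measure.

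**Working it through.** **Inputs from the protocol.** 385 completed surveys per cohort (section 3.5), with a range of 385-446 (Figure 7); 21 covariates, 12 clinical and 9 demographic or sociodemographic (Appendix 4); screen at p<0.1 (section 4.5).

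**Assumptions, not in the protocol.** An illustrative test level of 0.05, a two-sample normal approximation with equal variances, and the design effects d.

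**1. The plan's own figure.** n = 1.96² × 0.5 × 0.5 / 0.05² = 384.15, rounded up to 385. This reproduces section 3.5.

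**2. How much imbalance gives p>0.05.** With z = SMD × √(n_eff/2) and n_eff = n/d, the SMD at p=0.05 is 1.96 × √(2/n_eff).

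| n per cohort | d | n_eff | SMD at p=0.05 |
|---|---|---|---|
| 385 | 1 | 385 | 0.141 |
| 446 | 1 | 446 | 0.131 |
| 385 | 1.17 | 329 | 0.153 |
| 385 | 1.25 | 308 | 0.158 |
| 385 | 1.5 | 257 | 0.173 |

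For a covariate with 50% prevalence, an SMD of 0.141 is 0.141 × 0.5 = 7.1 percentage points. A true SMD of 0.10 would reach p<0.05 at 385 per cohort only about 28% of the time.

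**3. The same imbalance before and after weighting.** Hold the SMD at 0.15, with n=385 and a variance that reflects the weights.

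| d | z | p |
|---|---|---|
| 1 (unweighted) | 2.08 | 0.037 |
| 1.17 | 1.92 | 0.054 |
| 1.25 | 1.86 | 0.063 |
| 1.5 | 1.70 | 0.089 |

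Significance disappears although balance has not changed. With weights scaled to cohort size and no variance correction, p stays near 0.037. If unscaled weights were treated as counts (about 770 per cohort), an unchanged SMD of 0.13 would move the other way, from p=0.071 to p=0.011.

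The value 1.17 is the mean design effect in a simulation of 200 runs with 770 patients, 21 covariates, a correctly specified main-effects propensity model and weights scaled to cohort size. The mean SMD there was 0.132 before weighting and 0.012 after, with none above 0.10 after. The settings are assumed. Values of 1.25-1.5 stand for stronger treatment selection than was simulated.

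**4. Effect on the adjusted outcome models.** At n=770 (df=768), a covariate that just fails the p<0.1 screen has |r| = t/√(df + t²) = 1.647/√(768 + 2.71) = 0.059 with the score. If it is left out with an SMD of 0.15, the bias is about 0.15 × 0.059 = 0.009 SD. The difference detectable with 80% power is (1.96 + 0.84) × √(2/385) = 0.202 SD, so the bias is about 4% of it. At n=892 the figures are 0.15 × 0.055 = 0.008 SD against 0.188 SD, again about 4%. These are approximate values for one covariate, based on a marginal correlation. They do not bound the total over 21 covariates.

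**5. Weighted contrasts without further adjustment.** Here the screen gives no protection. An SMD of 0.14 on a covariate with an assumed correlation of 0.3-0.5 with the score shifts the contrast by 0.14 × 0.3 = 0.04 to 0.14 × 0.5 = 0.07 SD, or 21-35% of 0.202 SD.

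**The case against.** The best case for the plan has four parts.

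- **The list of checks is open.** The propensity diagnostics are examples, and the table shells are not in the supplied text, so a balance column may exist there. That stands against any claim that no balance measure is planned. The supplied text commits to none.
- **The review is wider than p-values.** Appendix 4 speaks of descriptive results, and section 4.3 lists means, standard deviations and percents, from which an SMD can be calculated. That is fair. But section 4.4 names the p-values as what is compared, section 4.3 says nothing about weighted results, and no limit is attached to either.
- **No pass rule is stated.** A reader might infer that the plan treats p>0.05 as proof of balance. It does not say so. The 0.05 level and the resulting SMD limits are illustrations, as is the 0.10 limit suggested below.
- **The practical effect may be slight.** With a correct propensity model the simulated residual imbalance was negligible, and the section 4.5 screen brings strong predictors into the models anyway. This stands for the adjusted models. It assumes the correct specification that a balance check exists to test; overlap and goodness of fit look at the propensity model but not at each covariate.

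A reader might also infer that the primary comparison is seriously biased. The documents do not support that: nothing in them shows that imbalance will remain, and the estimated effect on the adjusted models is small.

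**Conclusion.** The point holds as a weakness in a stated method that is worth correcting. It does not invalidate the comparison. Section 4.4 sets balance as the goal and names, for individual covariates, a before/after measure that does not show balance. How far p moves also depends on a variance method that is not stated. The size of that movement depends on the design effect: slight at the simulated 1.17 and larger at 1.25-1.5.

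The expected consequence for the covariate-adjusted CAT and mMRC models is modest, provided the section 4.5 screen is applied. Weighted results shown without further adjustment are more exposed. Whether they will be shown is not settled: the synopsis places modelling after review of the IPTW results, while section 4.4 can be read as weighting only within the model.

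**What to change.** In section 4.4, replace the p-value comparison, or at least supplement it, with absolute standardised differences before and after weighting for every Appendix 4 covariate, by level for categorical ones. Fix the limit in the SAP; 0.10 is an example and an assumption. State the action too: if the limit is exceeded, re-specify the propensity model before CAT and mMRC results by cohort are reviewed, and carry any covariate still above the limit into both outcome models. Reporting the effective sample size per cohort is useful but optional.

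The cost is a few lines of SAP text, one extra table from standard code, possibly a few more covariates in the two models, and a short re-specification step if it is triggered. No new data are needed.
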